11.2.2 Primary Safety Hypothesis

A PG of 55% was also established for the primary safety hypothesis test. There were two parts to establishing the PG:

1. Determining which values on an 11-point NRS scale correspond to mild pain and which to moderate.
2. Determining what percentage of subjects with no-to-moderate pain through 7-days is minimally acceptable for a cosmetic procedure.

The first part was answered by Boonstra et al (2016)²⁰, who showed that on a 11-point NRS, cut-off points of 5 for mild pain and 7 for moderate pain were appropriate. The second part was answered by Broughton et al (2006)²³, who estimated that approximately 55% of subjects reported no-to-moderate pain during the first week post-procedure.

The Broughton estimate was taken from Table 3 of the journal article (see **Table 7**), which tabulated the percentages of patients reporting pain levels following liposuction by time following the procedure and number of treatment areas. Using the data for subjects receiving treatment in 1-2 areas, we found that 53.4% of subjects reported no higher than moderate pain during the first week post-procedure:

Table 7: Excerpt of Table 3 Broughton article

Table 3: 1-2 Areas Liposuctioned					
Discomfort Level by Final Report (per Subject)					
	None	Mild	Moderate	Severe*	TOTAL
1 day	0.023	0.023			
2-3 days		0.093	0.047		
4-7 days		0.209	0.139	0.047	
TOTAL	0.023	0.325	0.186	0.047	.534
> 7 days*	0.023	0.093	0.093	0.209	0.418

* Gray cells not used in calculations.

Therefore, we set our PG at 55%. The null hypothesis test is that Renuvion APR results in fewer than 55% of subjects with maximal pain of “moderate” (NRS pain score of 7 or less) during the first week post-procedure (i.e., more than 45% have severe pain). The alternative is that more than 55% have moderate or less pain (NRS pain score of 7 or less) immediately post-procedure and at the 1-day and 7-day follow-up visits, and fewer than 45% have severe pain.

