11.1.2 Primary Safety Hypothesis Test

The sample size was also calculated for the primary safety hypothesis. Coincidentally, the parameters were identical to those for the primary effectiveness hypothesis, so the sample size was an identical test.

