7.2.2 Primary Safety Hypothesis

A PG of 55% was also established for the primary safety hypothesis test. There were two parts to establishing the PG:

1. Determining which values on an 11-point NRS scale correspond to mild pain and which to moderate.
2. Determining what percentage of patients with no-to-moderate pain through 7-days is minimally acceptable for a cosmetic procedure.

The first part was answered by Boonstra et al (2016)³, who showed that on a 11-point NRS, cut-off points of 5 for mild pain and 7 for moderate pain were appropriate. The second part was answered by Broughton et al (2006)⁴, who estimated that approximately 55% of subjects reported no-to-moderate pain during the first week post-procedure.

The Broughton estimate was taken from Table 3 of the journal article (see **Table 4**), which tabulated the percentages of patients reporting pain levels following liposuction by time following the procedure and number of treatment areas. Using the data for subjects receiving treatment in 1-2 areas, we found that 53.4% of subjects reported no higher than moderate pain during the first week post-procedure:

² Clopper, C.; Pearson, E. S. (1934). "The use of confidence or fiducial limits illustrated in the case of the binomial". *Biometrika*. 26 (4): 404–413. doi:10.1093/biomet/26.4.404

³ Boonstra AM, Stewart RE, Koke AJA, et al. Cut-Off Points for Mild, Moderate, and Severe Pain on the Numeric Rating Scale for Pain in Patients with Chronic Musculoskeletal Pain: Variability and Influence of Sex and Catastrophizing. *Front Psychol* 2016; 7: 1466.

⁴ Broughton G II, Horton B, Kipschitz A, et al. Lifestyle Outcomes, Satisfaction, and Attitudes of Patients after Liposuction: A Dallas Experience. *Plast. Reconstr. Surg.* 2006; 117: 1738-1749.

Table 4: Exert of Table 3 Broughton article

Table 3: 1-2 Areas Liposuctioned

Discomfort Level by Final Report (per Subject)

	None	Mild	Moderate	Severe*	TOTAL
1 day	0.023	0.023			
2-3 days		0.093	0.047		
4-7 days		0.209	0.139	0.047	
TOTAL	0.023	0.325	0.186	0.047	.534
> 7 days*	0.023	0.093	0.093	0.209	0.418

* Gray cells not used in calculations.

Therefore, we set our PG at 55%. The null hypothesis test is that Renuvion APR results in fewer than 55% of subjects with maximal pain of “moderate” during the first week post-procedure (i.e., more than 45% have severe pain). The alternative is that more than 55% have moderate or less pain, and fewer than 45% have severe pain.

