9.3 Statistical Analysis of Primary Safety Endpoint

NRS Pain through the 7-day Follow-up Visit

The 11-point NRS is used to measure facial, submental, and neck pain prior to procedure, within 60 minutes of treatment and at all follow-up visits. Note that the pain scale is 11 points: 0 through 10. The 0 value represents no pain. Levels 1 through 5 represent mild pain and levels 6 and 7 represent moderate pain. Patients who experience pain no higher than 7 through the 7-day visit post-procedure will be classified as “acceptable pain” patients.

For the primary safety endpoint, the proportion of patients with acceptable pain (P) will be tested against the PG. If the lower bound of the two-sided 95% confidence interval of the proportion of subject achieving treatment successes is greater than the Performance Goal, the primary safety endpoint would be met. The statistical test will be a one-sided Fisher’s Exact Test at $\alpha = 0.05$. For the primary safety endpoint to be met, H_0 must be rejected.

$$H_0: P \leq 55\% \quad \text{vs.} \quad H_a: P > 55\%$$

Standard descriptive statistics will also be reported; see **Section 9.1** for a list of descriptive statistics.

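### The 53.4% behind the 55% safety goal is not shown to be a first-week rate: the > 7 days row is left out of the numerator but kept in the denominator

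*Protocol*

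**What the plan says.** The primary safety test asks whether the proportion of subjects with none-to-moderate pain exceeds 55%. SAP 9.3 defines the endpoint by the highest score: "Patients who experience pain no higher than 7 through the 7-day visit post-procedure will be classified as" having acceptable pain.

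Protocol 11.2.2 derives the goal in two parts. The second part is "Determining what percentage of subjects with no-to-moderate pain through 7-days is minimally acceptable for a cosmetic procedure". The Protocol says that the cited liposuction survey answered this, because it "estimated that approximately 55% of subjects reported no-to-moderate pain during the first week post-procedure". It then gives the underlying figure, from subjects treated in one or two areas: "we found that 53.4% of subjects reported no higher than moderate pain during the first week post-procedure". The goal of 55% follows directly. SAP 7.2.2 repeats the argument and the table.

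The excerpt (Protocol Table 7, SAP Table 4) is headed "Discomfort Level by Final Report (per Subject". It has rows for 1 day, 2-3 days, 4-7 days and > 7 days, and columns from none to severe. The > 7 days row and the severe column are asterisked, with the note "Gray cells not used in calculations". Neither document says what a row means, when the level was measured, or how many subjects the survey had.

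**The concern.** A subject in the > 7 days row also went through the first week. A first-week rate for all subjects has to place these people somewhere, using what is known of their first-week pain. A rate for the other subjects has to remove them from both parts of the fraction. The plan does neither. It drops the row from the numerator while each cell remains a share of all subjects.

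This matters because the trial has one arm (SAP 3), so the goal is its only comparator for pain, and no other derivation of the safety goal is given. The plan may set a goal as a floor below a benchmark. Here, though, 55% is presented as what the survey found. A reader of the final report could take a pass to mean that pain compared well with the cited procedure.

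**Working it through.** **Inputs.** All cells are from Protocol Table 7, identical to SAP Table 4.

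| Row | None | Mild | Moderate | Severe | None to moderate | All levels |
|---|---|---|---|---|---|---|
| 1 day | 0.023 | 0.023 | | | 0.046 | 0.046 |
| 2-3 days | | 0.093 | 0.047 | | 0.140 | 0.140 |
| 4-7 days | | 0.209 | 0.139 | 0.047 | 0.348 | 0.395 |
| Rows to 7 days | 0.023 | 0.325 | 0.186 | 0.047 | 0.534 | 0.581 |
| > 7 days | 0.023 | 0.093 | 0.093 | 0.209 | 0.209 | 0.418 |

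The last two columns are row sums worked out here. The plan prints only 0.534 and 0.418 as totals.

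**Step 1: reproduce the plan's figure.** 0.023 + 0.325 + 0.186 = 0.534. This matches.

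**Step 2: find the denominator.** The rows to 7 days sum to 0.581. Adding the > 7 days row gives 0.581 + 0.418 = 0.999, which is 1 apart from rounding. Each cell is therefore a share of all subjects, including those in the > 7 days row.

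**Step 3: see what the 53.4% leaves out.** 0.999 − 0.534 = 0.465. It consists of:
- severe, rows to 7 days: 0.047
- severe, > 7 days: 0.209
- none to moderate, > 7 days: 0.023 + 0.093 + 0.093 = 0.209

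So 20.9% of subjects are recorded as none, mild or moderate but are not counted as such. (The severe cell of that row is also 0.209, by coincidence.)

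**Step 4: ask when 53.4% would be a first-week rate.** Take the earlier rows at face value. The rate equals 0.534 only if all of the 0.418 in the > 7 days row were severe in week 1, including the 2.3% recorded with no discomfort. Neither document says so.

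**Step 5: treat the row consistently.**
- Counted in both places: 0.534 + 0.209 = 0.743, or 74.3% (recorded severe: 0.047 + 0.209 = 25.6%).
- Removed from both: 0.534 / 0.581 = 91.9%. This describes a selected subset, not all treated subjects.
- First-week level of those subjects unknown, earlier rows at face value: from 0.534 (all severe) to 0.534 + 0.418 = 0.952, or 53.4% to 95.2%.

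If the heading means that the level is the one at the subject's final report, the excerpt gives no first-week rate at all.

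**The case against.** The sum is right, and the footnote discloses that the row was not used. The survey itself is not available here, and 53.4% is the lower end of the last range in the working, so it cannot be called impossible. The goal is described as a minimum, it was rounded up from 53.4% to 55%, and neither document claims superiority to liposuction. The observed proportion and its 95% confidence interval will be reported in any case (SAP 9.1 and 9.3).

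Most of this stands, and it limits the point to a figure that is not shown to be what it is called. Disclosing an exclusion does not explain the denominator, however, and rounding up by 1.6 points does not address it. The text also says that the survey answered what is minimally acceptable, which ties the goal to the figure.

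A reader might make two stronger inferences that the documents do not support.
- *That the plan wrongly reports more than 45% of survey subjects as severe.* The phrase "more than 45% have severe pain" belongs to the null hypothesis for the study device. The endpoint has two outcomes, so the complement of none-to-moderate is severe by definition. It is not a statement about the survey.
- *That the true benchmark is 74.3% or 91.9%, so the goal is too low and the trial underpowered.* Protocol 11.1.2 says that "the parameters were identical to those for the primary effectiveness hypothesis", which implies an assumed rate of 75%, close to 74.3%. But 74.3% is a first-week benchmark only under a reading of the rows and levels that the excerpt does not confirm.

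**Conclusion.** The point holds in a limited form. It is certain from the printed cells that the > 7 days subjects (41.8%) are in the denominator, while their none-to-moderate share (20.9% of all subjects) is not in the numerator. The 53.4% is therefore not shown to be a first-week rate, and the only stated basis for the safety goal does not support it. Consistent treatment of the row gives 74.3% or 91.9%, and leaving those subjects' first-week level open gives 53.4% to 95.2%. Each value depends on undefined rows and levels, and none is established as the benchmark.

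The consequence is for interpretation: passing would show that the proportion with acceptable pain is above a chosen floor, not that pain is at or better than with the cited procedure. The planned test can stand, so this should be fixed but does not invalidate the design. The significance level in SAP 9.3 and the confidence-limit convention in Protocol Table 6 are separate matters on which this point does not rely.

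**What to change.** In Protocol 11.2.2 and SAP 7.2.2, before Phase II pain data are reviewed:

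1. Withdraw the statement that 53.4% is a first-week rate, and the statement that the survey answered what is minimally acceptable.
2. State the status of the goal, for example: *The 55% goal is a minimum acceptable limit chosen by the sponsor. It is not an estimate from the cited survey.*
3. Give the survey proportion from the source with one denominator, its n, and the definition of the level and period it covers.
4. Limit the safety conclusion to pain being above a chosen floor, reported with the already planned observed proportion and 95% confidence interval.

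The null-hypothesis wording about severe pain may stay, as it concerns the study device.

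The cost is wording only: test, cutoff and sample size are unchanged. The price is a less favourable safety conclusion. If the sponsor prefers to re-derive the goal from a corrected benchmark, power must be restated at the same sample size. The documents do not fix that benchmark or the survey's n, so no power figure can be given here.

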11.3 Statistical Analysis

These analyses will be performed as follows. The primary effectiveness and primary safety objectives will include hypothesis tests which will be analyzed with Fisher’s exact test. All analyses of additional endpoints will be descriptive; standard descriptive statistics will be reported:

- Continuous variables (e.g. age) will be reported as the mean, number of observations, standard deviation, minimum, maximum, and 95% confidence interval (CI) of the mean.
- Categorical variables (e.g. sex) will be reported as the percentage and number of observations in each category and the 95% CI of the percentage.
- Time-to-event variables (e.g. time since last dose of anticoagulant drug) will be reported by the number at risk, the event rates over time and their 95% confidence intervals (CIs). Kaplan-Meier time-to-event analysis will be used to make the estimates.
- Count variables (e.g. number of hospitalizations in the last year) will be reported by the frequency and percentage in each count category, and the 95% CI of each. Poisson regression or negative binomial regression will be used to make the estimates; the method will depend on data dispersion.

Please refer to **Section 9.4** of the SAP for a detailed description of all analyses.

11.4 Subgroup Analysis

Differences in outcomes in age, sex, ethnicity, and body mass index will be explored if the number of study participants in each category is adequate to make such analysis feasible. Please refer to **Section 9.5** of the SAP.

12 DATA HANDLING AND RECORDKEEPING

12.1 Investigator Records

The Investigator is responsible for the preparation, review, signature, and retention of the following records:

- Signed Clinical Trial Agreement and Curriculum Vitae.
- All correspondence pertaining to the investigation with the reviewing IRB, the study Sponsor, and the Monitor.
- Subject case history records relating to use of the device, including Case Report Forms, medical records, progress notes, nurses' notes, etc.
- All signed informed consent forms.
- All shipping and disposition records for study devices and relevant observations relating to the use of the device.
- Relevant observations, including records concerning adverse events, condition of each subject upon entering and results of diagnostic tests.
- The protocol, amendments, and documentation of date and reason for any deviation from investigational plan.

12.2 Investigator Reports

The Investigator is responsible for the preparation, review, signature, and submission of the reports listed in **Table 8**. These are also subject to the FDA inspection and the retention requirements described above for the Investigator's Records.

Table 8: Required Investigator Reports

Report	Submit to	Description
Unanticipated Adverse Device Effect (UADE)	Sponsor and IRB	The Investigator must submit to the Sponsor and reviewing IRB a report of any UADE as soon as possible but not less than 10 working days after the Investigator first learns of the effect.
Withdrawal of IRB Approval	Sponsor	The Investigator must report a withdrawal of the reviewing IRB approval within 5 working days.
Progress Report	Sponsor, Monitor and IRB	The Investigator must submit this report at regular intervals, but not less than once per year to the IRB, Sponsor and Monitor.
Deviation from Protocol in Emergency	Sponsor and IRB	Deviation from the study protocol that is made to protect the life or physical well-being of a subject in an emergency situation must be reported within 5 working days after the emergency occurred.

Deviation from Protocol that affects the scientific soundness of the study plan or the rights, safety or welfare of human subjects	Sponsor	Prior approval by the Sponsor is required when a deviation of this nature is anticipated.
Failure to obtain informed consent	Sponsor and IRB	If a study device was used without obtaining informed consent, the Investigator must notify the Sponsor and IRB within 5 working days of the use of the device.
Final Report	Sponsor and IRB	The Investigator must submit this report to the Sponsor and IRB within 3 months after the termination or completion of the study, or after the Investigator's participation in the study is complete.

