8.3 Serious Adverse Event (SAE) Definition

Serious Adverse Event (SAE) is an adverse event that:

- Led to a death or
- Led to a serious deterioration in the health of a subject that:
 - Resulted in a life-threatening illness or injury,
 - Resulted in a permanent impairment of a body structure or body function,
 - Required in-patient hospitalization or prolongation of existing hospitalization,
 - Resulted in medical or surgical intervention to prevent impairment to body structure or a body function, or
 - Led to fetal distress, fetal death or a congenital abnormality or birth defect.

All SAEs that occur during the study period, whether considered to be related to the study device or not, must be reported to the Sponsor within 24 hours of knowledge of the event. IRB reporting requirements may also apply for SAEs.

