8.4 Unanticipated Adverse Device Effect (UADEs) Definition

An **unanticipated adverse device effect (UADEs)** is defined as any serious adverse effect on health or safety or any life-threatening problem or death caused by, or associated with, a device, if that effect, problem, or death was not previously identified in nature, severity, or degree of incidence in the investigational plan, or any other unanticipated serious problem associated with a device that relates to the rights, safety, or welfare of subjects.

In addition, any **UADEs** will be reported to the Sponsor and the reviewing IRB as soon as possible, but no later than within 24 hours of knowledge of the event.

All adverse events, anticipated or unanticipated, will be monitored until they are adequately resolved or explained.

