- To reduce the risk of dizziness and lightheadedness, get up slowly when rising from a sitting or lying position.

- **Tylenol**

A very serious allergic reaction to this drug is rare. However, get medical help right away if you notice any symptoms of a serious allergic reaction, including:

- Rash
- Itching/swelling
- Severe dizziness
- Trouble breathing

Other things to note:

This drug usually has no side effects. If you have any unusual effects, contact your doctor or pharmacist promptly.

Any unexpected or unforeseen complications will be managed by the investigator throughout the conduct of the study. Unforeseen or unexpected side effects not listed above will be reported to the sponsor and regulatory representatives (IRB) as they occur.

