10.4 Device Malfunction/Observations

All malfunctions of, or defects of the delivery system will be recorded on the Device Malfunction/Observation Case Report Form and reported to the Sponsor by the investigational sites. This will include situations where the delivery system did not perform as intended; user errors; study device/component being physically defective, including out of the box failure.

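### Table 8 sets the UADE report at not less than 10 working days, against a 24-hour maximum in Protocol 8.4 for the same event and recipients

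*Protocol*

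**What the plan says.** Two parts of the protocol set a time limit for reporting a UADE.

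- **Section 8.4** defines the UADE and requires any such event to be reported to the sponsor and the reviewing IRB "as soon as possible, but no later than within 24 hours of knowledge of the event". Its definition extends beyond serious health effects to "any other unanticipated serious problem associated with a device that relates to the rights, safety, or welfare of subjects".
- **Section 12.2, Table 8** lists the reports the investigator must prepare, sign and submit. Its UADE row also names the sponsor and the reviewing IRB, also covers any UADE, and gives the timing as "as soon as possible but not less than 10 working days after the Investigator first learns of the effect".

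Three other sections bear on the point.

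- **Section 8.3:** every SAE "must be reported to the Sponsor within 24 hours of knowledge of the event". For the IRB it says only "IRB reporting requirements may also apply for SAEs".
- **Section 9.2:** "Unforeseen or unexpected side effects not listed above will be reported to the sponsor and regulatory representatives (IRB) as they occur".
- **Section 10.4:** malfunctions and defects are "recorded on the Device Malfunction/Observation Case Report Form and reported to the Sponsor by the investigational sites", with no time limit.

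**The concern.** The event, the recipients and the starting point (when the investigator learns of it) match in 8.4 and Table 8, but the limits do not. Taken at its word, Table 8 sets an earliest date rather than a deadline, which also clashes with the opening of its own sentence asking for speed. Table 8 is the protocol's list of required investigator reports, and 12.2 says these are open to FDA inspection, so a site could reasonably take its deadlines from there.

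Two things are at stake for a site that does so.

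1. **IRB notice.** Section 8.3 gives no IRB time limit and 9.2 gives no number of hours. Section 8.4 is therefore the only numeric limit for prompt IRB notice, and Table 8 contradicts it. Under 10.6.1 an IRB recommendation can end or suspend the study, so the timing of that notice matters.
2. **Sponsor notice of a UADE that is not an SAE.** The last limb of the 8.4 definition can be met without the serious deterioration in health that 8.3 requires. The 24-hour SAE rule then does not apply, 9.2 covers side effects only, and the 10.4 report is untimed.

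There is also a compliance problem. Under 10.5 the monitor checks that AEs and SAEs were reported within the required periods, and for UADEs the protocol states two.

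**Working it through.** No design figure is involved, so the check is a comparison of the two rules and a day count.

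**Side by side**

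| | Section 8.4 | Table 8, UADE row |
|---|---|---|
| Event | any UADE | any UADE |
| Recipients | sponsor and reviewing IRB | sponsor and reviewing IRB |
| Clock starts | knowledge of the event | investigator first learns of the effect |
| Limit as written | at most 24 hours | at least 10 working days |

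**Literal reading.** The permitted windows are up to 24 hours, and 10 working days onward. They do not overlap.

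**Charitable reading.** Take the Table 8 phrase as *not later than*. Both limits are then maxima, and a report within 24 hours meets both. The gap between them follows from counting 10 working days from the day after knowledge, with no public holidays:

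| Day learned | Table 8 limit, calendar days | Minus 1 day in 8.4 |
|---|---|---|
| Monday to Friday | 14 | 14 − 1 = 13 |
| Saturday | 13 | 13 − 1 = 12 |
| Sunday | 12 | 12 − 1 = 11 |

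On this reading Table 8 allows 11 to 13 days more than 8.4. A public holiday would lengthen the Table 8 limit.

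**Within Table 8.** The row on IRB approval reads "The Investigator must report a withdrawal of the reviewing IRB approval within 5 working days". The rows for an emergency deviation and for missing informed consent also give 5 working days. The UADE row gives 10 / 5 = 2 times as long.

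**Which text is out of line.** Only 8.4 conflicts with Table 8 directly. The 24-hour SAE rule in 8.3 and the instruction in 9.2 to report as events occur both lean towards 8.4, so the direction of the correction is clear.

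**The case against.** The strongest reply is that this is a wording slip with little practical effect. A minimum delay makes no sense after a request for speed, and the Progress Report row of the same table uses *not less than* properly, for a yearly frequency, so the phrase may have been misapplied. The stricter limit is stated plainly in the safety section and names both recipients, so a site that follows 8.4 leaves no gap.

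The two rules may also describe different acts. Section 8.4 sits with adverse-event notification, while 12.2 sits under record-keeping and concerns signed documents. A 24-hour notice followed by a formal report within 10 working days would be a sensible arrangement.

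Much of this stands. The slip is the likely explanation, and the two-step process may be what was meant. Section 9.2 is weak evidence against Table 8 because it gives no hours and is compatible with reporting as soon as possible. The 5-working-day rows concern other matters, so they show only that the UADE row is slow by the table's own scale.

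The reply does not remove the inconsistency. Correcting the slip alone leaves 10 working days against 24 hours, and neither section separates a notice from a later report, refers to the other, or says which prevails.

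**Conclusion.** The concern holds. As written, the UADE row of Table 8 is incompatible with 8.4. On the charitable reading it still shows a limit 11 to 13 calendar days longer, assuming the count starts the day after knowledge and no holidays fall in the period. This is the distance between two stated limits and does not estimate an expected delay. The documents give no UADE rate, so how often it would matter cannot be computed, and no number of exposed subjects is claimed.

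The consequence is limited to safety reporting. Most UADEs are also SAEs and would still reach the sponsor within 24 hours under 8.3. What remains is prompt IRB notice, and sponsor notice of UADEs outside the SAE definition. The primary endpoints, sample size and analyses are untouched. The correction should be made, because a required-reports table should not carry a wrong safety deadline.

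**What to change.** In the UADE row of Table 8, replace the timing with that of 8.4: "as soon as possible, but no later than within 24 hours of knowledge of the event". If a fuller signed report is also wanted, add a separate line making it due no later than 10 working days after the investigator first learns of the effect, and state that it follows the 24-hour notice and does not replace it.

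The cost is one corrected table cell and, optionally, one added line. No new data, visits or analyses are needed.
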